**Figure 12-1 Candidate models for ensovibep dose**

- Dose-finding step – dose-response model fitting

A bootstrap sample (from a normal distribution with LS Means (Least Squares Means) and corresponding covariance matrix from an ANCOVA) is used to fit the non-linear dose-response functions and obtain parameter estimates for each model. Bootstrap model averaging based on AIC (Akaike Information Criterion) over all model families considered in the analysis will be used to estimate the final dose-response shape, to calculate the optimum dose(s) by substituting the values for the placebo-adjusted dose response in the model and solving for dose, and to derive the 95% CIs. Bootstrap simulation will be performed using the multivariate normal distribution of the adjusted estimates of the population means for each dose and generalized least-squares fitting of the resulting simulated values (Pinheiro 2014). The dose-response estimate will be the median across the bootstrap model predictions and 95% CIs based on bootstrap quantiles.

The dose suggested by MCP-Mod based on viral endpoint serves as an important consideration in dose selection. However, the final dose selection for Part B will be determined based on the following:

- Efficacy of doses based on rate of occurrence of hospitalizations ( $\geq 24$  hours of acute care) and/or emergency room visits related to COVID-19 or death from any cause up to Day 29, FDA modified symptom score; AND,
- Safety endpoints including ADAs (as available), AESIs, AEs, and SAEs.

## Part B

The primary objective of this Part is to demonstrate superiority of ensovibep, compared to placebo, in reducing the occurrence of hospitalizations ( $\geq 24$  hours of acute care) and/or emergency room visits related to COVID-19 or death from any cause up to Day 29.

The cumulative proportion of experiencing hospitalizations ( $\geq 24$  hours of acute care) and/or emergency room visits related to COVID-19 or death from any cause up to Day 29 will be estimated for each randomized group using Kaplan-Meier methods to take account of losses to follow-up.

The difference between randomized groups in the estimated log cumulative proportion will be calculated and the variance for this difference will be obtained using Greenwood's formula. Two-sided 95% CIs (adjusted for an interim analysis) and associated p-value for the test of no difference between groups will then be obtained.

The hazard ratios for these comparisons for the occurrence of hospitalizations ( $\geq 24$  hours of acute care) and/or emergency room visits related to COVID-19 or death from any cause and their corresponding 95% CIs will be computed using a stratified Cox proportional hazards regression model, stratified by baseline risk of progression to severe COVID-19 and/or hospitalization ("high risk" versus "not at high risk").

Time to hospitalizations ( $\geq 24$  hours of acute care) and/or emergency room visits related to COVID-19 or death from any cause will be presented graphically with a Kaplan-Meier plot.

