### **Stratification criteria**

Randomization will be stratified by risk of progression to severe COVID-19 and/or hospitalization: “high risk” or “not at high risk”. The stratum will be determined by the investigator according to below and entered into the interactive web response system (IWRS) at the time of randomization.

Patients will be considered “high risk” if they meet at least one of the following criteria:

- Have a body mass index (BMI)  $\geq 35$
- Have chronic kidney disease
- Have diabetes mellitus
- Have immunosuppressive disease
- Are currently receiving immunosuppressive treatment
- Are  $\geq 65$  years of age
- Are  $\geq 55$  years of age AND have
  - Cardiovascular disease, OR
  - Hypertension, OR
  - Chronic obstructive pulmonary disease/other chronic respiratory disease.

All patients not meeting the above high-risk criteria will be considered “not at high risk”.

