## Part B

Assuming the proportion of patients achieving the composite endpoint (of hospitalizations [ $\geq$  24 hours of acute care] and/or emergency room visits, related to COVID-19, or death from any cause) up to Day 29 is 6.5% based on [Gottlieb et al \(2021\)](#) in the placebo group and 50% reduction with to 3.25%, a sample size of 1717 patients 1:1 randomized to two treatment groups provides at least 90% power that the primary analysis will be statistically significant using a two-sided log rank test with 5% significance level assuming that the survival rates are exponential. These results assume that the group sequential design has one interim analysis for stopping the trial early for efficacy after 50% of patients complete Day 29 visit (two total analysis including final analysis) and the O'Brien-Fleming spending function is used to determine the efficacy test boundary.

Given possible enrichment for more severe COVID-19 cases, a range of operating characteristics were evaluated and presented in [Table 12-2](#).

Sample size calculations are performed in nQuery 8.4.1.0.

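### The Part B primary test ignores the risk stratum used in randomisation: it is valid but slightly conservative, and forgoes a small, almost free gain in precision

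*Protocol*

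**What the plan says.** **Randomisation.** Protocol 6.3.2 (Stratification criteria): "Randomization will be stratified by risk of progression to severe COVID-19 and/or hospitalization". There are two levels, high risk and not at high risk. Protocol section 3 and SAP 1.1 repeat this for Part B.

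**Primary test.** Protocol 12.4.2, Part B, says that the cumulative event proportion to Day 29 "will be estimated for each randomized group using Kaplan-Meier methods to take account of losses to follow-up". It continues: "The difference between randomized groups in the estimated log cumulative proportion will be calculated". Greenwood's formula supplies the variance, and the confidence interval and p-value come from that difference. SAP 2.5.2, Part B, says the same. Neither mentions the stratum at this step.

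**Where the stratum is used.** In the same section the hazard ratios "will be computed using a stratified Cox proportional hazards regression model, stratified by baseline risk of progression to severe COVID-19 and/or hospitalization". Protocol 12.4.6 adds a subgroup evaluation by risk. In Part A, the primary ANCOVA does adjust for this factor.

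**Sizing.** Protocol 12.8.1 sizes Part B "using a two-sided log rank test with 5% significance level assuming that the survival rates are exponential". The log-rank test is not described as stratified.

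**Status.** SAP sections 1 and 2.5 give only an outline for Part B and promise an amendment before its first patient is enrolled.

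**The concern.** Stratified 1:1 randomisation balances high-risk and other patients between arms, so differences in event risk between strata contribute almost nothing to the chance variation of the arm difference. A pooled Greenwood variance still counts that component. The standard error is then too large whenever the strata differ in risk. They are expected to differ: the factor is defined as risk of progression or hospitalisation, and hospitalisation is part of the endpoint.

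At stake is some precision in the test that decides Part B, with an interval slightly wider than the design warrants. The plan uses the stratum for the companion hazard ratio and for the Part A primary model, but gives no reason for omitting it here.

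**Working it through.** **1. Inputs.** From Protocol 12.8.1: placebo proportion "up to Day 29 is 6.5% based on" a cited trial, and "50% reduction with to 3.25%, a sample size of 1717 patients 1:1 randomized to two treatment groups provides at least 90% power". That is 858.5 patients per arm. From Protocol 12.7: one interim at 50% with bound Z = 2.963. The matching O'Brien-Fleming-type final bound is 1.969. No dropout rate is stated, so I take none; Greenwood variance then reduces to p(1 − p)/n. I read the test statistic as the difference in log event proportions.

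*Assumed, because the documents give no figures:* share s of high-risk patients 20% to 70%; ratio r of high-risk to low-risk event rates 2 to 5, plus an extreme of 8; overall placebo rate fixed at 6.5%; risk halved in both strata.

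**2. The plan's own figure.** HR = ln(1 − 0.0325)/ln(1 − 0.065) = 0.4916. Expected events = 858.5 × (0.065 + 0.0325) = 83.7. Schoenfeld's formula with the two bounds gives N = 1716 and, at 1717, power 90.02%. Table 12-2 is reproduced with no stratification gain in it.

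**3. Variance used by the planned test** (log scale):
(1 − 0.065)/(858.5 × 0.065) + (1 − 0.0325)/(858.5 × 0.0325) = 0.01676 + 0.03468 = 0.05143.
Power on this scale with no stratum effect is 86.2%.

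**4. Actual variance under stratified randomisation.** Low-risk placebo rate = 0.065/(s·r + 1 − s); high-risk rate = r times that; drug rates are half of each. For each arm with overall rate P, the log-scale variance is [s·p_H(1 − p_H) + (1 − s)·p_L(1 − p_L)]/(n·P²).

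Example, s = 0.2, r = 5:
- Placebo rates are 18.06% and 3.61%; drug rates 9.03% and 1.81%.
- Placebo arm: 0.05744/(858.5 × 0.065²) = 0.01584.
- Drug arm: 0.03061/(858.5 × 0.0325²) = 0.03376.
- Sum 0.04959; ratio 0.05143/0.04959 = 1.037.
- Patient equivalent: 1717 × (1 − 0.04959/0.05143) ≈ 61.

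**5. Type I error.** This must use the variance ratio under the null, with both arms at 6.5%. In the example it is 0.065 × 0.935/0.05744 = 1.058. The effective cut-off is 1.96 × √1.058 = 2.016, so the two-sided error is 4.4%.

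**6. Results**, planned test against the stratum-standardised test, N = 1717, with the interim:

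| High-risk share | Ratio | Placebo rates, high / low | Variance ratio | Patients | Power gain (points) | Type I error |
|---|---|---|---|---|---|---|
| 70% | 2 | 7.6% / 3.8% | 1.003 | 6 | 0.07 | 4.9% |
| 20% | 2 | 10.8% / 5.4% | 1.005 | 9 | 0.11 | 4.9% |
| 50% | 3 | 9.8% / 3.3% | 1.011 | 19 | 0.25 | 4.8% |
| 30% | 3 | 12.2% / 4.1% | 1.015 | 25 | 0.32 | 4.7% |
| 50% | 5 | 10.8% / 2.2% | 1.021 | 35 | 0.44 | 4.6% |
| 30% | 5 | 14.8% / 3.0% | 1.032 | 54 | 0.68 | 4.4% |
| 20% | 5 | 18.1% / 3.6% | 1.037 | 61 | 0.77 | 4.4% |
| 20% | 8 | 21.7% / 2.7% | 1.066 | 106 | 1.31 | 3.9% |

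With equal risk in both strata there is no loss.

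**7. Simulation check** (200,000 trials, no interim, s = 0.3, r = 3): power 88.5% unstratified against 88.8% standardised; type I error 4.5% against 4.8%. With no stratum effect the unstratified test already runs at 4.8%, so part of the conservatism belongs to the log-scale Wald test itself.

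**The case against.** **The test is valid and matches the estimand.** The Part B summary measure is a marginal comparison of proportions, which pooled Kaplan-Meier estimates target directly. Type I error stays below 5%. This stands: the issue is efficiency only. It is not a reason to remain unstratified, because weighting stratum-specific proportions by the overall stratum shares targets the same marginal quantity.

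**The size rests on assumptions.** This also stands. At a 6.5% event rate, within-stratum binomial variation dominates, and the largest figures need a 20% share with an eightfold risk ratio.

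**A reader might infer that the planned 90% power is eroded.** The documents do not support that. The 90.02% reproduces from a log-rank calculation without any stratification gain, so leaving out the stratum forgoes a bonus. The 86.2% baseline above arises because the trial is sized on one test and analysed with another. That is a separate and larger matter.

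**A reader might call the stratified Cox model a contradiction.** It is not. It estimates a conditional hazard ratio, a different quantity, and may reasonably be stratified by itself.

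**Simplicity has some value.** With about 84 events, cells can be sparse. At a 70% share and ratio 8, the low-risk drug cell expects 858.5 × 0.3 × 0.0055 ≈ 1.4 events. It has none with probability about 24% at the final analysis and 49% at the interim, and its Greenwood variance is then zero. Simulation showed no type I inflation from this, but a rule is needed.

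**Conclusion.** The point holds as a minor efficiency and consistency issue. The Part B primary test omits the factor by which patients are randomised, and its variance is overstated whenever the strata differ in event risk. For ratios of 2 to 5 the overstatement is 0.3% to 3.7%, worth about 6 to 61 patients and 0.1 to 0.8 power points, with true type I error about 4.4% to 4.9%. The extreme case reaches 6.6%, 106 patients, 1.3 points and 3.9%.

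These sizes depend on assumed stratum shares and rates, an equal relative effect in both strata, and no dropout. The direction needs only a difference in event risk between strata. Nothing here makes the test invalid or reduces the power that the sample size calculation claims.

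**What to change.** In Protocol 12.4.2 (Part B) and the Part B SAP amendment:

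1. Estimate the Day 29 Kaplan-Meier event proportion and Greenwood variance by arm within each risk stratum.
2. Combine them in each arm with the overall stratum shares, both arms together, as weights. The variance is the sum of squared weights times the stratum variances; divide it by the squared standardised proportion for the log scale.
3. Base the primary contrast, confidence interval and p-value on these standardised proportions at both the interim and the final analysis, and carry the same statistic into the separate interim analysis plan.
4. State which stratum value is used. Protocol 6.3.2 has the investigator enter it at randomisation, while SAP 2.1.1.9 programs it from eCRF data and compares the two; they may differ.
5. Fall back to the pooled estimate if any stratum-by-arm cell has no events.

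The marginal estimand and sample size are unchanged. The cost is a few sentences in an amendment that is already planned and a few lines of code. It should be settled before any unblinded Part B data exist, since changing the primary statistic after that would be hard to defend.

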#### **12.4.3 Handling of remaining intercurrent events of primary estimand**

##### **Part A**

A combination of treatment policy and composite strategy will be used to handle the intercurrent events.

A treatment policy will be used to handle (1) post-treatment initiation of all antivirals (including convalescent serum, antiviral antibodies, and antiviral small molecules) and immunosuppressive medications; and, (2) post-treatment increase in dose of immunosuppressive medications, for the treatment or management of COVID-19, and a patient will be evaluated regardless of experiencing either of these intercurrent events.

A composite strategy will be used to handle (3) death from any cause and (4) COVID-19 related hospitalization. In the event a patient experiences death or COVID-19 related hospitalization, all values after the time of death/start of the COVID-19 related hospitalization for change from baseline in log10 SARS-CoV-2 viral load will be set as the worst observed value based on observed values at each time point within each treatment arm independently.

##### **Part B**

A treatment policy will be used to handle (1) post-treatment initiation of all antivirals (including convalescent serum, antiviral antibodies, and antiviral small molecules) and immunosuppressive medications; and, (2) post-treatment increase in dose of immunosuppressive medications, for the treatment or management of COVID-19, and a patient will be evaluated regardless of experiencing either of these intercurrent events.

#### **12.4.4 Handling of missing values not related to intercurrent event**

##### **Part A**

Missing measurement in log10 SARS-CoV-2 viral load will be imputed using last observation carried forward (LOCF) approach.

##### **Part B**

Patients who prematurely discontinue the study and whose outcomes after discontinuation are not ascertainable will have follow up censored at the date of last known status.

#### **12.4.5 Supplementary analysis**

##### **Part A**

A supplemental analysis:

- excluding patients who experienced a negative PCR COVID-19 test following a positive swab; and,
- using multiple imputation to handle the missing data will be performed.

Further details on supplementary analyses can be found in the SAP.

##### **Part B**

Simple event rate estimates (proportion of events) will be presented for the primary composite efficacy endpoint.

An alternative estimand may be considered with a composite strategy account for the intercurrent events of (1) post-treatment initiation of all antivirals (including convalescent serum, antiviral antibodies and antiviral small molecules), ambulatory oxygen, and immunomodulating or immunosuppressive medications; and, (2) post-treatment increase in dose of ambulatory oxygen, and immunomodulating or immunosuppressive medications, for the treatment or management of COVID-19. The primary endpoint will be considered a failure at the time of the intercurrent event.

The primary efficacy analysis may be repeated excluding patients who experienced a negative PCR COVID-19 test following a positive swab.

A tipping point analysis will be conducted to assess the impact of the missing data strategy in [Section 12.4.4](#).

Additional analyses to address sensitivity of assumptions may be performed including inverse probability of censoring modeling.

Further details on supplementary analyses can be found in the SAP.

#### **12.4.6 Supportive analysis**

The subgroup evaluation of baseline risk of progression to severe COVID-19 and/or hospitalization (“high risk” versus “not at high risk”) on ensovibep will be performed for both Parts. Further details on supportive analyses will be specified in the SAP.

### **12.5 Analysis of secondary endpoints**

For all secondary objectives analysis details are described in the SAP.

#### **12.5.1 Efficacy endpoints**

##### **12.5.1.1 Hospitalizations ( $\geq$ 24 hours of acute care) and/or emergency room visits related to COVID-19 or death from any cause**

This secondary objective applies only to Part A. In Part B, this endpoint is the primary objective. For handling of the secondary analysis on the proportion of patients experiencing hospitalizations ( $\geq$  24 hours of acute care) and/or emergency room visits related to COVID-19 or death from any cause up to Day 29, see details in the SAP.

##### **12.5.1.2 SARS-CoV-2 Viral load**

This secondary objective applies only to Part B. In Part A, this endpoint is the primary objective. For handling of the secondary analysis on log10 SARS-CoV-2 viral load in nasopharyngeal swabs through Day 8, see details in [Section 12.4](#).

##### **12.5.1.3 COVID-19 symptoms**

Acute COVID-19 symptoms will be collected up to Day 29 to evaluate the efficacy of ensovibep using a COVID-19 symptoms collection tool containing a 14 symptoms questionnaire, collectively referred to as the FDA COVID-19 questionnaire ([FDA 2020a](#)). This questionnaire will be an eCOA tool completed by the patient. Each of the symptoms is rated on a scale of 0 to 3: 0 – none, 1 – mild, 2 – moderate, 3 – severe.

Sustained clinical recovery is defined as (a) all symptoms from the modified FDA COVID-19 symptom list scored as moderate or severe at baseline are subsequently scored as mild or absent, AND (b) all symptoms from the modified FDA COVID-19 symptom list scored as mild or absent at baseline are subsequently scored as absent, with no subsequent worsening, up to Day 29.

The cumulative proportion of achieving sustained clinical recovery up to Day 29 will be estimated for each randomized group using Kaplan-Meier methods to take account of losses to follow-up. Patients who prematurely discontinue the study and whose outcomes after discontinuation are not ascertainable will have follow up censored at the date of last known status.

The difference between randomized groups in the estimated log cumulative proportion will be calculated and the variance for this difference will be obtained using Greenwood’s formula.

Two-sided 95% CIs and associated p-value for the test of no difference between groups will then be obtained.

Time to sustained clinical recovery will be presented graphically with a Kaplan-Meier plot. A Cox proportional hazards model will be used, stratified by baseline risk of progression to severe COVID-19 and/or hospitalization (“high risk” versus “not at high risk”).

## 12.5.2 Safety endpoints

### Adverse events

Adverse events (AEs) are to be coded with the MedDRA dictionary that gives PT and primary SOC information. The number (and percentage) of patients with treatment emergent

- AEs
- SAEs
- AESIs (see [Section 10.1.4](#))

will be summarized for each Part by:

- treatment, SOC, and PT;
- treatment, SOC, PT, and CTCAE; and,
- treatment, Standardized MedDRA Query (SMQ) and PT.

Treatment-emergent deaths will be summarized for each Part by treatment, SOC, and PT.

A patient with multiple AEs within a primary SOC will be only counted once towards the total of the primary SOC.

AEs and SAEs will be summarized for each Part by treatment and treatment-emergent ADAs (TE-ADA) status as defined in [Section 10.1.1](#).

AEs of Special Interest are defined in [Section 10.1.4](#).

- The number (and percentage) of patients with each of the AESIs will be summarized for each Part by treatment and by treatment and maximum severity.

### Vital signs

All vital signs data will be summarized by treatment in each Part at Day 1, Day 3, Day 5, Day 8, Day 29, and Day 91. Changes from baseline to values at each time point will be summarized for each Part by treatment. Patients with abnormalities will be listed.

[figure not shown]
A complete list of the vital sign parameters will be provided in the SAP.

### Clinical laboratory evaluations

All laboratory data, including hematology and biochemistry data, will be summarized by treatment in each Part at Day 1, Day 5, Day 8, Day 29, and Day 91. Changes from baseline to values at each time point will be summarized for each Part by treatment. Shift tables using the

low/normal/high/ (low and high) classification will be used to compare baseline to the worst on-treatment value. Patients with abnormalities will be listed.

A complete list of the laboratory parameters, including hematology and biochemistry parameters, will be provided in the SAP.

## **12.7 Interim analysis**

An external IDMC will be established and perform review as defined in [Section 10.3](#). The details of the analysis required for IDMC will be specified in a separate IDMC charter and analysis plan.

## Part A

No interim analysis will be performed for the efficacy evaluation. Analysis of primary endpoint will be carried out when all patients have completed the Day 29 visit (or withdrawn prematurely) and have viral load data up to Day 8. Final analyses of Part A will occur when all patients have completed Day 91 visit (or withdrawn prematurely). However, analyses of primary endpoint will not be repeated.

## Part B

There is one interim analysis after at least 50% of patients complete Day 29 and one final analysis after at least 1717 patients have completed Day 91. The interim analysis permits early stopping due to efficacy controlling overall type I error rate. The interim analysis upper stopping bound in Z scale is 2.963 (corresponding to alpha is 0.03).

Further details will be provided in a separate Interim Analysis SAP.

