Figure 2-1	Candidate models for ensovibep dose.....	25

List of abbreviations

ADA	Anti-Drug Antibody
AE	Adverse Event
AESI	Adverse Event of Special Interest
ANCOVA	Analysis of Covariance
COVID-19	Coronavirus Disease 2019
CSR	Clinical Study Report
CTCAE	Common Toxicity Criteria for Adverse Events
DBL	Database Lock
eCRF	Electronic Case Report Form
eCRS	Electronic Case Retrieval Sheet
FAS	Full Analysis Set
FDA	Food and Drug Administration
FPFV	First Patient First Visit
IA	Interim Analyses
IDMC	Independent Data Monitoring Committee
IRR	Infusion-related Reactions
ITT	Intention-to-treat
MCS	Mental Component Summary
MedDRA	Medical Dictionary for Drug Regulatory Affairs
PCS	Physical Component Summary
PD	Pharmacodynamics
PK	Pharmacokinetics
PP	Per-Protocol
PRO	Patient-Reported Outcomes
PT	Preferred Term
RAN	Randomized Set
RT-PCR	Real Time Polymerase Chain Reaction
SAE	Serious Adverse Event
SAP	Statistical Analysis Plan
SAS	Statistical Analysis System
SARS-CoV-2	Severe Acute Respiratory Syndrome Coronavirus 2
SCR	Screened Set
SF-36	Short Form 36 Health Survey Questionnaire
SMQ	Standard MedDRA Query
SOC	System Organ Class
SS	Safety Set
TEAE	Treatment-emergent Adverse Event

1 Introduction

This document presents the detailed statistical analysis plan (SAP) for Study MP0420-CP302 (CSKO136A12201J), “A randomized, double-blind, placebo-controlled, multicenter study of ensovibep (MP0420) in ambulatory adult patients with symptomatic COVID-19.”

Following the operationally seamless design, analysis of Part A and Part B will be handled separately (e.g., primary, secondary, and exploratory analyses in Part A will be performed only on Part A patients and primary, secondary, and exploratory analyses in Part B will be performed only on Part B patients).

This SAP will include the details for the clinical study report (CSR) analysis of Part A and Part B. In this version, the full details for the CSR analysis of Part A is provided. An outline of the protocol-specified CSR analysis of Part B is provided in the SAP. Further details will be provided in a SAP amendment prior to first patient first visit (FPFV) of Part B.

The analysis for Part A is performed in two parts:

- **Part A primary analysis:** performed when all patients enrolled completed Day 29 or discontinued prematurely and have viral load data up to Day 8; the analysis will include available data on the day of cutoff. Further details are provided in [Section 2.14](#).

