1.1 Study design

This is a randomized, double-blind, placebo-controlled, multicenter study of ensovibep (MP0420) in ambulatory patients with symptomatic COVID-19. The study has two parts: A Phase 2 dose-ranging study to select the best dose over the therapeutic range (Part A) and a confirmatory Phase 3 safety and efficacy study of the dose determined in Part A (Part B).

Screening will be used to determine eligibility. Randomization and treatment will be conducted on Day 1 (screening can optionally be done up to 3 days earlier, or also at Day 1) and with a study duration for individual patients of 91 ± 7 days for both Parts.

Part A

[figure not shown]
This dose-ranging part of the study will include approximately 400 randomized patients in four arms (3 active arms and one placebo arm), randomized 1:1:1:1 (see also [Figure 1-1](#)) to receive ensovibep (75 mg, 225 mg, or 600 mg) or placebo, administered as a single i.v. infusion over

60 minutes, and stratified by risk for COVID-19 disease progression (“high-risk”, “not at high-risk”)..

Part B

Recruitment will begin in Part B once the best safe and efficacious dose has been selected from Part A based on Day 29 data analysis. Part B will include at least 1717 patients randomized 1:1 (see also [Figure 1-1](#)) to either the selected dose of ensovibep or placebo, administered as i.v. infusion over 60 minutes. An interim analysis for early efficacy will be conducted when approximately 50% of patients have completed the Day 29 assessments. Patients will be stratified by risk for COVID-19 disease progression (“high-risk patients” versus “not at high-risk patients”).

Figure 1-1 Study design

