3.1 Primary endpoint(s)

Part A

In Documentation for the EUA for emergency use of casirivimab and imdevimab, issued 21 Nov 2020, it is shown that the treatment effect in time-weighted change from baseline (Day 1) to Day 8 of \log_{10} SARS-CoV-2 viral load in nasopharyngeal swabs was -0.36 for the overall population and -0.68 for the subgroup of patients with at least 10^7 copies at baseline and the estimated standard deviation was between 1.0 and 1.2.

Assuming the published evidence to be predictive over 8 days, a sample size of at least 100 patients per treatment group, for a total of 400 patients, would have at least 80% power (minimum power over the considered candidate shapes) with a one-sided Type I error rate of 0.10 to detect a dose-response trend versus placebo using MCP-Mod to select the smallest dose for consideration in the decision to move into Part B.

The power calculation given the range of operating characteristics (treatment effect: -0.36, -0.68, and standard deviation: 1, 1.1, 1.2) were performed based on MCP-Mod in R (Pinheiro 2006) and are presented in [Table 3.1-1](#).

Table 3.1-1 Power for Part A given a range of operating characteristics given 400 patients, 100 patients in each arm and a one sided significance level of 10%

Treatment Effect	Standard Deviation	Power (%)
-0.36	1	90.03
	1.1	85.25
	1.2	80.25
-0.68	1	99.98
	1.1	99.92
	1.2	99.73

Part B

Assuming the proportion of patients achieving the composite endpoint (of hospitalizations (\geq 24 hours of acute care) and/or emergency room visits, related to COVID-19, or death from any cause) up to Day 29 is 6.5% based on [Gottlieb et al \(2021\)](#) in the placebo group and 50% reduction with to 3.25%, a sample size of 1717 patients 1:1 randomized to two treatment groups provides at least 90% power that the primary analysis will be statistically significant using a two-sided log rank test with 5% significance level assuming that the survival rates are exponential. These results assume that the group sequential design has one interim analysis for

stopping the trial early for efficacy after 50% of patients complete Day 29 visit (two total analysis including final analysis) and the O'Brien-Fleming spending function is used to determine the efficacy test boundary.

Given possible enrichment for more severe COVID-19 cases, a range of operating characteristics were evaluated and presented in [Table 3.1-2](#).

Sample size calculations are performed in nQuery 8.4.1.0.

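### Part B interim efficacy bound: Z = 2.963 is labelled alpha 0.03, but it is a nominal alpha of 0.003 two-sided (0.0015 one-sided)

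*Protocol*

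**What the plan says.** Protocol 12.7 (Interim analysis, Part B) and SAP 2.14 (Interim analysis, Part B) contain the same sentence: "The interim analysis upper stopping bound in Z scale is 2.963 (corresponding to alpha is 0.03". Both place it directly after the statement that the overall type I error rate is controlled. Neither document gives another interim alpha.

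The design behind the bound is in Protocol 12.8.1 and SAP 3.1. The sample size "provides at least 90% power that the primary analysis will be statistically significant using a two-sided log rank test with 5% significance level", with one interim look after half the patients complete Day 29 and a final analysis. An O'Brien-Fleming "spending function is used to determine the efficacy test boundary".

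The timing of the look is worded differently in different places. Protocol 12.7 says "There is one interim analysis after at least 50% of patients complete Day 29", while SAP 1.1 says "An interim analysis for early efficacy will be conducted when approximately 50% of patients have completed the Day 29 assessments".

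Both documents leave further Part B detail for later: Protocol 12.7 to a separate interim analysis plan, and SAP section 1 to an amendment ("Further details will be provided in a SAP amendment prior to first patient first visit (FPFV) of Part B").

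**The concern.** A Z bound and its nominal alpha are the same threshold on two scales, so each fixes the other. Here they differ about tenfold on the two-sided alpha scale. The sentence is the only numerical statement of when the confirmatory part may stop early for efficacy. Someone who programs or reads the rule on the p-value scale would take 0.03, and that is a much easier hurdle than the one the design was built on.

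**Working it through.** **Inputs.** Z = 2.963 and alpha = 0.03 (Protocol 12.7, SAP 2.14). Two-sided 5%, so 0.025 per side; O'Brien-Fleming spending; one look at half the information, t = 0.5; event rates 6.5% and 3.25%; 1717 patients randomized 1:1 (Protocol 12.8.1, SAP 3.1). I take the spending function to be the Lan-DeMets O'Brien-Fleming type.

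**1. Does the design give the stated Z?** Spend per side is 2 × [1 − Φ(z₀.₀₁₂₅/√t)], with z₀.₀₁₂₅ = 2.2414.

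- At t = 0.5: 2.2414/√0.5 = 3.170, and the spend is 0.001525 per side, or 0.00305 two-sided.
- The interim bound is the Z with upper tail 0.001525, which is 2.9626. The plan's 2.963 is reproduced.
- The final bound c solves P(Z₁ < 2.9626, Z₂ < c) = 0.975 with correlation √0.5. This gives c = 1.9686 (two-sided p = 0.0490).

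**2. Does the same design give the stated power?** Use the log-rank model with exponential survival.

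- Events: 858.5 × (0.065 + 0.0325) = 83.7.
- Hazard ratio: ln(0.9675)/ln(0.935) = 0.4916.
- Drift: −ln(0.4916) × √(83.7/4) = 3.248.
- Power with bounds 2.9626 and 1.9686: 90.02%. Protocol Table 12-2 and SAP Table 3.1-2 also give 90.02%.

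So the Z value, the sample size and the power belong to one consistent design.

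**3. Does Z = 2.963 correspond to 0.03?**

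- Two-sided: 2 × [1 − Φ(2.963)] = 0.003047. Ratio 0.03/0.003047 ≈ 9.8.
- One-sided: 1 − Φ(2.963) = 0.001523. Ratio 0.03/0.001523 ≈ 19.7.
- In reverse, 0.03 is Z = 2.170 two-sided or 1.881 one-sided.

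**4. Can 0.03 be read another way?**

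| Reading | Result |
|---|---|
| Cumulative alpha spent, two-sided | At a first look this equals the nominal alpha, 0.00305. A spend of 0.03 needs t = (2.2414/2.4324)² = 0.849 |
| Cumulative alpha spent, one-sided | 0.03 exceeds the whole 0.025 |
| Spending function applied to 0.05 directly | 0.0056 at t = 0.5 |
| Classical two-stage O'Brien-Fleming | Z = 2.797, two-sided alpha about 0.005 |

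None of these gives 0.03 with Z = 2.963.

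**5. What if 0.03 were applied?** This is hypothetical, at t = 0.5, with two-sided 0.03 (Z = 2.170) used at the interim.

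- Final bound kept at 1.969: P(Z₁ > 2.170 or Z₂ > 1.969) = 3.35% in the efficacy direction, against 2.5%.
- Final bound re-derived to hold 2.5%: it rises to 2.187, and power falls from 90.0% to 87.0% under the log-rank planning model.

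**The case against.** The best case on the other side concerns weight. The rule is stated on the Z scale and that number is correct; 0.03 is a gloss in brackets, probably with a zero lost. The 5% level, the spending function and the commitment to control overall type I error all point a statistician back to 2.963. The Part B text is openly provisional, and the interim would be run under later documents. The error and power figures in step 5 require someone to set aside the stated Z and use 0.03 in its place. All of this stands, and it makes misuse less likely. It does not make 0.03 correct: deferral explains missing detail, but here a wrong number is already in the current text of both documents.

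Two limits also stand. First, 2.963 is the right bound only at an information fraction of 0.5. The spending function gives 2.806 at 0.55 and 2.669 at 0.60, and the share of patients past Day 29 need not equal the share of events. Second, the power figures rest on the log-rank planning model, while the stated primary test in Protocol 12.4.2 is different: "The difference between randomized groups in the estimated log cumulative proportion will be calculated". They are not exact for that test. Neither limit makes Z = 2.963 equal to an alpha of 0.03.

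**Conclusion.** The stated alpha is wrong as written in both documents. The mismatch in step 3 depends only on the normal distribution. That the alpha, and not the Z, is the wrong figure rests on the design in Protocol 12.8.1 and SAP 3.1, which reproduces both the bound and the tabulated power at an information fraction of 0.5. It should be corrected because it sits in a confirmatory stopping rule, but there is no defect in the bound or the sample size. The consequences in step 5 are illustrations, not expected outcomes.

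**What to change.** In Protocol 12.7 and SAP 2.14, replace the alpha of 0.03 with a two-sided nominal alpha of 0.003 (one-sided 0.0015). Printing 0.00305 is slightly better: 0.003 two-sided converts back to Z = 2.968, whereas 0.00305 gives 2.963. Nothing else is required.

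If the sponsor chooses to add the final bound, it should be labelled as the planned value at information fraction 0.5 (Z = 1.969, two-sided p = 0.049), with a statement that both bounds are recomputed from the spending function at the fraction actually reached.

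The cost is one number in each document, with no change to the Z bound, sample size, patients or data. The SAP amendment already promised before the first Part B patient could carry the SAP correction.
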